4.0 STUDY AIMS AND HYPOTHESES

Primary Outcome

The primary outcome is composite STI incidence at 6-month follow-up in which a person is considered positive for STIs if they are positive on any tested STI.

Secondary Outcomes

Secondary outcomes include self-reported sexual risk behavior, being under the influence of substance and/or illicit drug use during sexual activity and cost and cost-effectiveness. The sexual risk and substance use behavior secondary outcomes will be measured at baseline and six months post-randomization as the self-reported number of unprotected sex acts (vaginal and/or anal sex without a condom) and sex while high on drugs or alcohol, which will be measured as the number of sexual occasions when substance use was involved. The cost analysis will consider the budgetary perspective of STD clinics, because decision makers in these programs may be unwilling to implement HIV counseling and testing unless they are reimbursed for costs according to their clinic's budgetary guidelines. The cost-effectiveness analysis will be conducted from the societal perspective (Hall et al., 2008), taking into account the time and expenses incurred by participants. Cost-effectiveness from payer perspectives will be considered in secondary analyses.

4.1 **Primary Aim and Hypothesis**

Aim 1: To determine the effectiveness of brief, participant-tailored prevention counseling in reducing STI incidence among patients seeking medical or health services at STD clinics

H1: The incidence of STIs among participants offered an HIV test with counseling will differ from participants offered an HIV test with information only.

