10.5 Overview of Analysis Plan

The primary outcome will be analyzed using logistic regression for the binary outcome, new diagnoses of STIs (Yes/No). The logistic regression analysis will predict 6-month STI incidence as a function of randomization group controlling for the baseline incidence of STI. The test of the

hypothesis will be based on a likelihood ratio test comparing the model with and without the indicator for randomization group.

ANCOVA will be used for the secondary continuous outcomes, number of sexual risk behaviors and number of sexual episodes involving substance use. For example, the number of sexual risk behaviors at 6 months will be the outcome and the level of sexual risk behaviors at the baseline assessment will be the only covariate. The STI outcome, the test of the hypothesis will be based on an ANCOVA type specification test comparing models with and without the randomization group indicator. Costs will be compared based on study records supplemented by site-level data collection as described above. All analyses will be performed under intent-to treat (ITT) criteria.

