The planned subgroup analyses will test for differences between sets of subgroups (MSM versus non-MSM, African American versus all other race/ethnic groups, men versus women, young (<25) versus older) on the difference in rates of STI by treatment status. Planned exploratory analyses will calculate effect-sizes for subgroups, defined by MSM, heterosexual male, female, all racial/ethnic categories, presence of STI at baseline and use of (any) substances during sex at baseline. Planned exploratory analyses will also examine the extent to which the covariates explain variability in outcomes. First, the baseline levels of condom use self-efficacy, substance use/abuse and depression will be assessed for any potential moderating (interaction) effects on the hypothesized outcomes. Second, the impact of the intervention on these same set of variables will be assessed. For any of these covariates that are affected by the intervention, additional analyses will examine the relationship between changes in these potential mediators and study outcomes. Note that true tests of mediation are not possible due to the lack of temporal precedence in these changes. Prior to all analyses the distributions of outcomes will be examined and the appropriateness of planned analysis strategies assessed. For example, sexual risk and drug use frequently have the characteristics of a count variable. If this is the case, the ANCOVA framework will be utilized within the context of a Poisson, Zero-inflated Poisson or a Negative Binomial model, depending on which has the best fit to the data.

Missing data is a ubiquitous problem in human subject research, primarily due to dropping out and refusal. Missing data can lead to biased estimates and reduction of power, impacting the generalizability of the study. While we will make every effort to minimize the amount of missing data, in follow-up analyses we will attempt to assess the impact of the missing observations. Missingness patterns will be identified and analyses will be conducted to determine if there is a differential attrition by treatment arm, and if missingness is related to any of the covariates. If nonrandom missingness is of concern, this problem can be addressed by applying propensityscore matching so that the impact of bias can be assessed.

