10.6 Statistical Power and Sample Size Calculation

All power calculations assume that the Type I error rate, α , is .05. Power calculations for main effects for treatment were made with PASS 2005. Power for interaction effects was calculated using a simulation program written in SAS 9.1.3. The original RESPECT study showed a significant effect of 6-month rate of new STIs which were 7.2% in the counseling arm and 10.4% in the didactic arm, for a difference of 3.2%. Though underpowered to be definitive, subgroup analysis of RESPECT-2 suggested that there is a differential effect of counseling on MSM compared to heterosexuals.

We therefore decided to power this study both to uncover a risk difference of 3.2% (with a higher base rate of STI incidence of 12.0%) and to have sufficient power to test for an interaction between MSM and non-MSM in which the ratio of risk ratios was approximately 2.0. Simulations showed that to have over 80% power for both the 3.2% risk difference overall and a 2 fold risk ratio interaction between MSM and other study participants required 1663 per group or 3326 total sample at the six month assessment. Although we anticipate closer to 85% follow-up, we used the conservative assumption of 70% retention for calculation of power. With the assumption of 70% retention, this means that 5000 must be randomized. Simulations assumed that 1/3 of the participants were MSM. Power for other, separate sub-group comparisons should be similar to that described above for MSM vs. non-MSM as long as the smaller subgroup in the comparison approaches or exceeds a third of the sample composition, which is consistent with the data we have obtained from the sites. For the secondary hypotheses of sexual risk behavior and substance use during sex there will be over 80% power to uncover a standardized difference between groups of .10, which is considered a small effect.

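### Picking Poisson, zero-inflated Poisson or negative binomial by best fit leaves the behavioral treatment effect undefined if the zero-inflated model wins, and does not by itself give a valid test

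*Protocol*

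**What the plan says.** Protocol section 10.5 makes ANCOVA, with the baseline value as the only covariate, the default for the behavioral outcomes. The distributions are to be looked at first. If an outcome behaves like a count, the same framework is carried into a Poisson, ZIP or negative binomial model, "depending on which has the best fit to the data". No fit criterion is named.

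The only test described for these outcomes is a specification test "comparing models with and without the randomization group indicator". The sentence is garbled: it opens by naming the STI outcome and then describes an ANCOVA-type test.

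Three of the four example outcomes in section 10.4.1 are six-month counts of acts or partners, so the switch is the likely path. Section 10.6 states power for these outcomes in standard-deviation units: "there will be over 80% power to uncover a standardized difference between groups of .10".

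**The concern.** Two things depend on which family wins.

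**What is estimated.** ANCOVA estimates a difference in means. Poisson and negative binomial with a log link estimate a ratio of means. ZIP estimates an odds ratio for being a structural zero and a rate ratio among the remaining participants. The protocol does not say which ZIP parameter is the treatment effect. Counseling could plausibly work by moving people to no unprotected acts at all, which the ZIP count part does not capture.

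**Whether the test is valid.** The best of three candidates can still misstate the variance. Counts of sex acts may well have both excess zeros and long tails, and none of the three families has separate parameters for both.

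At stake are the p-values and the effect reported for the self-reported behavioral outcomes. The primary STI analysis is a logistic regression and is not affected.

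**Working it through.** **Inputs.** From section 10.6: "All power calculations assume that the Type I error rate, α , is .05", and the design "required 1663 per group or 3326 total sample at the six month assessment". The hypothesis in section 4.1 is non-directional ("will differ from participants offered an HIV test with information only"), so tests are two-sided. The protocol gives no mean, variance or share of zeros for any count, so every distribution below is an assumption.

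**1. The plan's own figure.** Power for a standardized difference of 0.10 with 1,663 per arm is Φ(0.10 × √(1663/2) − 1.96) = Φ(2.884 − 1.960) = Φ(0.924) = 82.2%. The number needed for 80% is 2 × (1.960 + 0.842)² / 0.10² ≈ 1,570 per arm. The stated figure of over 80% is reproduced. It describes a mean difference, not a count-model effect.

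**2. Estimand under ZIP.** Take 30% structural zeros in the control arm.
- Five points more abstainers, same rate among the rest: overall mean ratio 0.65/0.70 = 0.93, count-part ratio 1.00. In simulation ZIP was chosen, its count-part test rejected 4.5%, and the robust ratio-of-means test rejected 67%.
- Six points more abstainers and 6% more acts among the rest: overall ratio 0.64 × 1.06/0.70 = 0.97, a reduction. The selected ZIP count-part ratio is 1.06, an increase.

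**3. Why negative binomial can err either way.** Its single dispersion parameter *a* sets both the variance, m + a·m², and the zero share, (1 + a·m)^(−1/a). Two populations with 30% structural zeros and mean 20 among the rest both have overall mean 14.
- *Negative binomial counts among the rest, dispersion 0.5.* Variance = 0.7 × (20 + 200 + 400) − 14² = 238. Matching it needs a = (238 − 14)/196 = 1.14, which implies 8% zeros; the data have 31%. The fit raises *a*, overstates the variance, and the test is conservative.
- *Lognormal rates, log SD 1.5.* Variance = 0.7 × (20 + 400 × e^2.25) − 14² ≈ 2,475. Matching it needs a = (2,475 − 14)/196 ≈ 12.6, which implies 66% zeros; the data have 37%. The fit lowers *a*, understates the variance, and the test rejects too often.

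**4. Simulated type I error.** No true effect, 1,663 per arm, no covariate, 2,000 replicates per scenario, family chosen by lowest AIC, arm tested by likelihood ratio at 0.05 (Monte Carlo standard error about 0.5 points).

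| Assumed counts | Family chosen | Rejection |
|---|---|---|
| Zero-inflated negative binomial, 30-40% structural zeros, mean 20 | NB always | 0.1-0.5% |
| Lognormal, mean 4, log SD 1.2 (partner-like) | NB always | 14% |
| 30% structural zeros, lognormal, mean 20, log SD 1.5, heaped reporting | NB always | 18% |
| Same, not heaped | NB always | 22% |
| 10% structural zeros, lognormal, mean 15, log SD 1.7 | NB always | 35% |
| Zero-inflated, mild extra dispersion | ZIP in 69-100% | 9-11% |
| True negative binomial | NB | 5.8-5.9% |
| True ZIP | ZIP | 5.2% |

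One zero-inflated lognormal case with log SD 1.0 gave 4.9%. Poisson was never chosen. A prespecified ratio of means with robust variance rejected 4.5-6.1% across all 13 scenarios. In the four lognormal rows an ordinary comparison of means rejected 4.0-4.8%.

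Further runs agree. With 30% structural zeros, count mean 15 and dispersion 1, the negative binomial test rejected 1.5%, against 4.8% for the same model with robust variance. Fitting ZIP directly, without the selection step, to data with 40% zeros and mild overdispersion gave 13-17% for the count part.

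**5. With the baseline value as covariate** (250 replicates, standard error about 1.4 points; negative binomial and ZIP compared by log-likelihood). The selected model rejected 24% (long tail), 1.2% (excess zeros) and 11% (ZIP chosen). A log-link Poisson mean model with sandwich variance rejected 5.2%, 6.8% and 4.8%.

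**6. Cost in power.** In the mean-15 case, power for a 12% reduction was 61% with the likelihood-ratio test and 75% with robust variance. That reduction is 0.12 × 10.5/14.67 = 0.086 SD, a little below the 0.10 in the plan. With 5 points more abstainers in the zero-inflated negative binomial cases, power was 15-18% against 47-62%.

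**The case against.** Several points on the other side stand.

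- **The test is partly inferred.** Section 10.5 attaches no variance estimator to the count models, and the with/without-indicator sentence is garbled and precedes them. A reader might infer that the plan commits to model-based standard errors. It does not; robust variance is simply not mentioned.
- **Detail can be left to the statistical analysis plan.** The fit criterion, variance estimator and ZIP parameter commonly are, and the absence of each is not the complaint. The protocol itself does fix the rule that fit to the outcome data chooses the family.
- **A reader might infer that all three models estimate different things.** Poisson and negative binomial share the ratio of means. The estimand changes only with ZIP, or between ANCOVA and any count model.
- **A reader might infer that ZIP allows no single test of arm.** A joint two-degree-of-freedom test exists. Under true ZIP with mean 5 it had size 5.2%, and it rejected 76-78% with 5 points more abstainers, against 66-68% for the robust ratio of means. It gives no single directional effect, however, and it rejected 7-13% under assumed overdispersion.
- **A reader might infer that the error rates are always wrong.** They are near 5% when the chosen family is true. Poisson's understated variance matters little, because an AIC rule would rarely choose it.

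**Conclusion.** The concern holds in a limited form. The best-fit rule leaves the treatment effect undefined if ZIP wins, and it does not protect the test when negative binomial or ZIP wins but is not the true family. At nominal 5%, the plausible range runs from about 0.1-2% under excess zeros to 14-35% under long lognormal-type tails for negative binomial, and about 9-17% for the ZIP count part.

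These sizes rest on assumed distributions, on AIC or likelihood as the fit criterion, and on likelihood-ratio tests without robust variance. That the error can go either way follows from the variance arithmetic in step 3 and does not depend on one scenario. Better retention than assumed ("we used the conservative assumption of 70% retention for calculation of power") would not remove it, because the ratio of model variance to true variance does not shrink with sample size.

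Only self-reported secondary outcomes are affected. The change is worth making but does not bear on the primary conclusion.

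**What to change.** Before unblinding, prespecify for the count outcomes in section 10.4.1:

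- one estimand, the ratio of mean six-month counts between arms;
- one model, log-link negative binomial with arm and baseline value, fitted whatever the observed fit;
- one test of arm, using robust (sandwich) variance.

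Keep Poisson, zero-inflated and other count models as sensitivity analyses, and for ZIP state which parameter is reported. Outcome (d) in section 10.4.1, the share of acts involving drugs or alcohol, is a proportion and needs its own model. Repair the garbled test sentence in section 10.5 at the same time.

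The cost is a few sentences and no new data. The statistical price is a small loss of efficiency if another family were exactly true.

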5.5.2 Enhancement of Retention

To maintain high statistical power and maximize the generalizability of results, we aim to retain a minimum of 85% of the 5,000 randomized participants at the six-month follow-up point. A number of strategies will be employed in order to achieve these minimum retention rates. Participants will be asked to complete a Locator Information Form on which they will provide contact information for themselves and at least two friends or family members which will make it easier for us to locate them for follow-up appointments. Permission will also be requested to obtain locating information from additional databases. Locator information will be verified and updated regularly prior to the six-month follow-up visit and maintained at the site. Staff will provide mail and telephone reminders to participants.

In addition to providing reminders of upcoming follow-up visits via mail and telephone, reminders may be made via e-mail or text message according to participants' request and permission provided in the Locator Information form. In addition, staff will physically go to locations specified by participants on the Locator Information forms, as needed. Participant retention will be enhanced in several other ways as outlined below.

- We will employ one full-time retention specialist working across study sites that will track all participants' follow-up windows, monitor retention activities and work closely with research staff to ensure that they are conducting reminder and outreach activities according to specified follow-up windows. Additionally, the retention specialist will identify STD clinic-specific and cross-site barriers to retention and problem solve with STD clinic staff. This retention specialist will be based at the University of Miami and will keep the principal investigators and other co-investigators informed in the event that a higher level of intervention with a STD Clinic is needed.
- During the baseline visit, participants will receive a reminder card with the date and time of their next visit. Reminder cards will be discreet with regard to the nature and purpose of the study.
- We will provide each site with a computerized program to help them monitor the participants' windows and due dates for follow-up.
- Participants may be compensated for contacting research staff prior to their follow-up visit and confirming/updating their locator information.

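### Propensity-score matching, the one remedy named for nonrandom missingness, cannot correct or assess bias when missing 6-month STI results depend on the unseen result

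*Protocol*

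**What the plan says.** Protocol Section 10.5 sets the primary analysis as a logistic regression to "predict 6-month STI incidence as a function of randomization group controlling for the baseline incidence of STI", and adds: "All analyses will be performed under intent-to treat (ITT) criteria".

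Missing data come later in the same section, as secondary work: "in follow-up analyses we will attempt to assess the impact of the missing observations". Missingness patterns will be described, and analyses will be run "to determine if there is a differential attrition by treatment arm, and if missingness is related to any of the covariates". Then comes the one remedy: "If nonrandom missingness is of concern, this problem can be addressed by applying propensityscore matching so that the impact of bias can be assessed". The section does not say who is matched to whom, on which variables, or at what ratio.

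On the amount of missing data, Section 5.5.2 states a goal: "we aim to retain a minimum of 85% of the 5,000 randomized participants at the six-month follow-up point". Section 10.6 says "Although we anticipate closer to 85% follow-up", but for the sample size "we used the conservative assumption of 70% retention for calculation of power".

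**The concern.** A propensity score is a function of measured variables. Matching on it can balance those variables. It carries no information about the 6-month STI status of people who did not provide one, beyond what the measured variables already predict. If return depends on that status, matching leaves the bias in place and gives no measure of it.

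The checks that come before matching have the same limit. A test of attrition by arm sees only a difference in retention. A test of association with covariates cannot separate missingness driven by a covariate from missingness driven by the outcome that the covariate predicts. Outcome-dependent missingness that differs between arms at similar overall retention could pass the arm test, be left untouched by matching, and be reported as having been addressed.

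Such dependence is plausible here. Section 3.2 says that most STD clinic attendees come because of symptoms, contact with a symptomatic person, or a check-up. New symptoms could bring a participant back, or send the participant elsewhere for care, and counseling could change that response in one arm. The direction is unknown.

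**Working it through.** **The plan's own figures.** From Section 10.6: 12.0% against 8.8% (difference 3.2 points), alpha 0.05, 1,663 per group. The test is taken as two-sided because the hypothesis in Section 4.1 is non-directional. The mean rate is 0.104.

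- Null standard error: √(2 × 0.104 × 0.896 / 1663) = 0.01059.
- Alternative standard error: √((0.12 × 0.88 + 0.088 × 0.912) / 1663) = 0.01057.
- Power: Φ((0.032 − 1.96 × 0.01059) / 0.01057) = 85.6%, consistent with the stated figure of over 80%.
- Randomized number: 3326 / 0.70 = 4,752. The plan's 5,000 is larger, which is on the safe side.
- Missing outcomes out of 5,000: 0.15 × 5000 = 750 at the anticipated retention, 0.30 × 5000 = 1,500 at the planning value.

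**Bias at equal retention.** Assumptions, not in the protocol: no true effect, p = 0.12 in both arms, and the same overall missing proportion m in both arms. In one arm STI-positive participants are R times as likely to be missing as STI-negative ones; in the other arm missingness is unrelated to STI status. In the affected arm:

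- missing if negative: m₀ = m / (pR + 1 − p)
- missing if positive: m₁ = R × m₀
- observed rate: p(1 − m₁) / (1 − m)

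For R = 1.5, pR + 1 − p = 0.18 + 0.88 = 1.06.

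- m = 0.15: m₀ = 0.1415, m₁ = 0.2123, observed rate = 0.12 × 0.7877 / 0.85 = 11.12%. Bias 0.9 points.
- m = 0.30: m₀ = 0.2830, m₁ = 0.4245, observed rate = 0.12 × 0.5755 / 0.70 = 9.87%. Bias 2.1 points.

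| R | Bias, 15% missing | Bias, 30% missing | Chance of a significant result, 15% | Chance of a significant result, 30% |
|---|---|---|---|---|
| 1.25 | 0.45 points | 1.1 points | 6.6% | 17.4% |
| 1.5 | 0.9 points | 2.1 points | 14.4% | 52.5% |
| 2.0 | 1.7 points | 4.0 points | 40.6% | 97.9% |

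The last two columns should read 5% when there is no effect. The analyzed numbers per arm are 2500 × 0.85 = 2,125 and 2500 × 0.70 = 1,750. Retention is identical in both arms in every row, so a test of attrition by arm has nothing to find.

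**Does matching remove it?** A simulation of 300 trials of 5,000 used one observed covariate that affects both STI risk and missingness, no true effect, and extra missingness for STI-positive participants in one arm. Because the protocol gives no scheme, returners in one arm were matched 1:1 to returners in the other, with a caliper of 0.2 standard deviations of the logit propensity score.

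| Extra log-odds of missing | Overall missing | Complete-case bias | Weighted bias | Matched bias |
|---|---|---|---|---|
| 0 | 26.6% | 0.0 points | 0.0 points | 0.0 points |
| 0.7 | 27.6% | 2.4 points | 2.5 points | 2.4 points |
| 1.0 | 28.0% | 3.4 points | 3.5 points | 3.4 points |

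Neither matching nor inverse-probability weighting on the observed covariate removed any of the bias. Retention was not held equal in this simulation: the affected arm had about 2 × (27.56 − 26.63) = 1.9 points more missing at log-odds 0.7. Only the algebra above isolates the equal-retention case.

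**What a tipping-point analysis would show.** Suppose the observed difference is 3.2 points. The non-returners' STI rates would have to differ between arms, in the opposite direction, by 0.032 × (1 − m) / m to bring the overall difference to zero. That is 18.1 points at 15% missing and 7.5 points at 30%.

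**The case against.** **The word nonrandom.** The sentence before the remedy speaks of missingness related to arm and covariates. If that is what nonrandom means, a propensity method is a relevant tool. This stands, and it limits the point to outcome-dependent missingness. The protocol does not draw the distinction, though, and it names nothing for the other kind.

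**Status.** The step is conditional, sits in follow-up analyses, and aims to assess bias. It does not replace the primary test. This stands and keeps the point in proportion.

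**The bias needs an arm difference.** In a logistic model, if the chance of return given STI status is the same in both arms, the selection factors cancel from the complete-case odds ratio. On the risk-difference scale with R = 1.5 in both arms, a true 3.2 points would appear as 3.0 (15% missing) or 2.7 (30% missing). Serious bias therefore needs dependence that differs by arm. Nothing in the protocol shows that it will, and nothing planned could rule it out.

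**Stronger readings that the document does not support.**

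- A reader might infer that 15% to 30% missing is expected. Section 10.6 anticipates about 15%; 30% is a planning margin.
- A reader might infer that matching will discard randomized participants. That is a usual consequence, but no scheme is given. The simulated scheme lost about 1.5% to 2% of observed participants (3,622 to 3,569, and 3,602 to 3,530).
- A reader might infer that the primary model drops everyone without a 6-month visit result. Section 10.5 does not say so. Section 5.4.2 provides for abstraction of clinic records to evaluate outcomes, and Section 5.5.2 allows follow-up visits in the field.
- A reader might build the case on unequal retention, say 85% against 80%, with non-returners at twice the risk of returners: 0.12/1.15 = 10.43% against 0.12/1.20 = 10.00%, a false difference of 0.43 points. The planned attrition test would detect that gap: its standard error is √(0.85 × 0.15/2500 + 0.80 × 0.20/2500) = 1.07 points, so z is about 4.7. At equal retention that formula gives no bias.
- A reader might treat the absence of imputation or a tipping-point analysis as an omission. A protocol commonly leaves that to the SAP, which was not available here. The point is only that the method which is named cannot do what is said of it.

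**Conclusion.** The point holds for missingness that depends on the 6-month STI result. In that case the named remedy neither corrects the bias nor assesses it, and the planned checks cannot reveal it when retention is similar between arms. For missingness explained by measured covariates, a propensity method may help.

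The size depends on assumed inputs. With no true effect, 12% incidence, equal retention and a missingness ratio of 1.5 in one arm only, the bias is about 0.9 points at the anticipated 15% missing and 2.1 points at the planning value of 30%. These are 28% and 67% of the 3.2-point design difference (0.88/3.2 and 2.13/3.2). They are illustrations, not predictions. At 15% missing, a full 3.2-point observed effect would be fairly hard to overturn, which a tipping-point analysis would show and matching would not. This is a change worth making to a sensitivity analysis; it is not a fault in the primary test.

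**What to change.** In protocol Section 10.5, replace the matching sentence with two prespecified sensitivity analyses of the primary outcome, run regardless of the attrition tests:

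1. Multiple imputation of the 6-month composite by arm, or inverse-probability weighting, using the stratification factors (site, race/ethnicity, gender, and MSM or heterosexual among males), age, baseline STI and baseline risk behavior. This covers missingness explained by observed data.
2. A delta-adjusted tipping-point analysis that varies the odds of STI among non-returners separately by arm and reports where the conclusion changes. This covers outcome-dependent missingness.

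The first alone is not enough, because imputation and weighting also rely on observed data.

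The cost is a few days of programming. One limit should be stated: Section 5.4.3 has the baseline HSV-2 samples of participants lost to follow-up processed only if funding allows, so part of baseline STI status may be unavailable for some of them. The primary test, sample size and visits do not change.
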